6.3 Primary analysis

The primary analysis will be the main analysis that is planned around 5 months after last participant first dose.

6.4 Final analysis

The final analysis will be performed after end of study. An extract of the primary analysis as specified in the table of contents for TFLs will be created for the follow-up analysis after database lock.

7 Changes to the Planned Analyses in the Clinical Study Protocol

7.1 COVID-19 Impact

No changes to the planned analysis of the efficacy or safety endpoints are planned due to the impact of Coronavirus disease 2019 (COVID-19) outbreak. Sensitivity analyses may be considered depending on the observed COVID-19 findings.

Additional outputs (summary table and listing) will be generated for a description of the impact by COVID-19 on the study. The number and percentage of participants will be presented for the following findings due to COVID-19:

- Potentially affected by COVID-19
- Adverse Events
- Protocol deviations (important and non-important)
- Missed Visits (including number of missed visits)
- Missed efficacy evaluations (including number of missed efficacy evaluations)
- Tele-visits performed (including number of tele-visits)
- Drug administration - missed doses

- Drug administration - dose adjustments
- Laboratory testing performed by external laboratory unit (only if at least 10 participants are affected)
- Treatment discontinuation (of cetuximab and/or tepotinib)
- Study discontinuation
- Death

Potentially affected participants (either due to infection or due to circumstances of social distancing affecting the capabilities of sites/hospitals etc.) are defined as:

- a) Participants who started treatment after start of the COVID-19 pandemic, or
- b) Participants who started treatment prior to start of the COVID-19 pandemic and had tumor assessments planned after the start of the pandemic (i.e., did neither have progressive disease, died or withdrew from tumor assessments prior to start of the pandemic).

A frequency table will be produced for the Safety Analysis Set to present the number of participants with important protocol deviations related to COVID-19 (categorized by frequency of participants with an important protocol deviation overall as well as by category of protocol deviation and type of protocol deviation). A separate table for the non-important protocol deviations related to COVID-19 (categorized by frequency of subjects with a non-important protocol deviation overall as well as by category of protocol deviation) will also be produced.

In addition, separate listings of COVID-19 related adverse events and protocol deviations will also be produced.

Outputs related to disposition and exposure will be amended to present reason of treatment/study discontinuations due to COVID-19 and treatment delays due to COVID-19 (if possible).

Laboratory results performed by external laboratory units will be included in the summary statistics and shift analyses, provided that normal ranges are not missing; if they are missing, results will be listed and included in summary statistics outputs only.

8 Analysis Populations and Subgroups

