15.4 Clinical Laboratory Evaluation

Laboratory assessments such as hematology and coagulation, biochemistry, urinalysis and other screening tests (e.g.: pregnancy tests) will be performed by local laboratories.

Laboratory results will be classified according to the NCI-CTCAE criteria version 5.0. Additional laboratory results that are not part of NCI-CTCAE will be presented according to the categories: below normal limit, within normal limits and above normal limit (according to the laboratory normal ranges).

The last measurement before study treatment first dose (including unscheduled measurements) will serve as the baseline measurement. For further details about baseline and change from baseline, please refer to Section 9.2.

Values below the detection limit will be imputed by half of the detection limit.

In case just a text value with an “> x” is reported it will be analyzed as +1 significant digit, e.g. “> 7.2 mmol” will be analyzed as 7.3.

Quantitative data will be summarized using descriptive statistics (n, mean, StDev, median, Q1, Q3, minimum, and maximum) of actual values and absolute changes from baseline to each scheduled visit over time. Scheduled visits performed during the safety run-in are to be presented, too.

Qualitative data based on reference ranges will be described according to the categories Low, Normal, and High (Hematology, Biochemistry and Coagulation). For qualitative data of urinalysis measurements, the raw classifications Normal, Trace/+, ++, +++, +++++ will be used instead. Results from the urinalysis microscopic examination (Erythrocytes, Leukocytes, Epithelial cells, Bacteria, Crystals and Casts) will only be listed.

Abnormalities classified according to NCI-CTCAE toxicity grading version 5.0 will be described using the worst on-treatment grade. Measurements from both scheduled and unscheduled visits should be considered for the worst on-treatment grade derivation; also measurements performed during the safety run-in are to be taken into account. For those parameters which are graded with two directions of toxicities such as potassium (hypokalemia/hyperkalemia), the toxicities will be summarized separately. Low direction toxicity (e.g., hypokalemia) grades at baseline and post baseline will be set to 0 when the variables are derived for summarizing high direction toxicity (e.g., hyperkalemia), and vice versa.

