For **WBC differential counts** (total neutrophil [including bands], lymphocyte, monocyte, eosinophil, and basophil counts), the absolute value will be used when reported. When only percentages are available (this is mainly important for neutrophils and lymphocytes, because the NCI-CTC grading is based on the absolute counts), the absolute value is derived as follows:

$$\text{Derived differential absolute count} = (\text{WBC count}) * (\text{Differential \%value} / 100)$$

If the range for the differential absolute count is not available (only range for value in % is available) then Grade 1 will be attributed to as follows:

- Lymphocyte count decreased:
 - derived absolute count does not meet Grade 2-4 criteria, and
 - % value < % LLN value, and
 - derived absolute count $\geq 800/\text{mm}^3$
- Neutrophil count decreased
 - derived absolute count does not meet Grade 2-4 criteria, and
 - % value < % LLN value, and
 - derived absolute count $\geq 1500/\text{mm}^3$

For **calcium**, NCI-CTC grading is based on Corrected Calcium and Ionized Calcium (CALCIO), if available. Corrected Calcium is calculated from Albumin and Calcium as follows

$$\text{Corrected calcium (mmol/L)} = \text{measured total Calcium (mmol/L)} + 0.02 (40 - \text{serum albumin [g/L]})$$

where the albumin values should be taken from the same sample, analyzed in the same laboratory as calcium.

Liver function tests: Alanine aminotransferase (ALT), aspartate aminotransferase (AST), alkaline phosphatase (ALP) and total bilirubin (TBILI) are used to assess possible drug induced liver toxicity. The ratios of test result over upper limit of normal (ULN) will be calculated and classified for these three parameters during the on-treatment period.

Summary of liver function tests will include the following categories. The number and percentage of participants with each of the following during the on-treatment period will be summarized:

- ALT $\geq 3 \times$ ULN, ALT $\geq 5 \times$ ULN, ALT $\geq 10 \times$ ULN, ALT $\geq 20 \times$ ULN
- AST $\geq 3 \times$ ULN, AST $\geq 5 \times$ ULN, AST $\geq 10 \times$ ULN, AST $\geq 20 \times$ ULN
- (ALT or AST) $\geq 3 \times$ ULN, (ALT or AST) $\geq 5 \times$ ULN, (ALT or AST) $\geq 10 \times$ ULN, (ALT or AST) $\geq 20 \times$ ULN
- TBILI $\geq 2 \times$ ULN
- Concurrent ALT $\geq 3 \times$ ULN and TBILI $\geq 2 \times$ ULN
- Concurrent AST $\geq 3 \times$ ULN and TBILI $\geq 2 \times$ ULN

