Laboratory toxicities will be tabulated (count and percentage) for each gradable parameter by the worst on-treatment NCI-CTC grade. For selected parameters with the on-treatment grading depending on baseline grading (as indicated in Appendix 1), the worst on-treatment grade will be tabulated by the status at baseline (normal or abnormal). Shifts from baseline to worst NCI-CTC grade during the on-treatment period will also be tabulated. The denominator to calculate percentages for each laboratory parameter is the number of participants in each analyzed group. Participants without baseline or on-treatment post-baseline results for a given parameter will be presented in the “Missing” category and will contribute to the denominator.

Please see [Appendix 1](#) for a list of the NCI-CTC -gradable parameters.

Parameters with NCI-CTC grades not available:

Laboratory abnormalities will be tabulated (count and percentage) for each non-gradable parameter by the worst on-treatment abnormality. Shift tables from baseline to each time point as well as to worst abnormality during the on-treatment period will also be tabulated. For each parameter, the shift to the maximum post-baseline as well as the minimum post-baseline value will be presented. The denominator to calculate percentages for each laboratory parameter is the number of participants in each analyzed group. Participants without baseline or post-baseline results for a given parameter will be presented in the “Missing” category and will contribute to the denominator.

Following figures will be provided for each above-mentioned test:

- Boxplots of the laboratory values by time point.
- Boxplots of the change from baseline by time point.

Boxplots for laboratory parameters where toxicity grades are defined based on the ratio of the parameter values and the upper limit of normal (ULN) will not be displayed using the unit of measurement but instead using the ratio of the measured value over ULN. This comprises ALP, ALT, AST, bilirubin, creatinine.

The listings of laboratory results will be provided for all laboratory parameters. The listings will be sorted by parameters and assessment dates or visits for each participant. Laboratory values that are outside the normal range will be flagged in the data listings, along with corresponding normal ranges and CTCAE grades.

Results from pregnancy tests, both serum and urine, collected on the “Pregnancy Test” eCRF page will be listed.

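### SAP 7.1 keeps external-laboratory results without normal ranges out of the shift-to-worst-grade tables even where the grade needs no range, as for low neutrophil and lymphocyte counts at Grade 2 to 4

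*SAP*

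**What the plan says.** SAP 7.1 (COVID-19 Impact) sets the rule for laboratory tests done by external units. Their results "will be included in the summary statistics and shift analyses, provided that normal ranges are not missing"; otherwise "if they are missing, results will be listed and included in summary statistics outputs only". The condition applies to all parameters, with no exception for grades that do not depend on a range.

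SAP 15.4 (Clinical Laboratory Evaluation) describes the tables. For gradable parameters there are two outputs. One is a frequency table: "Laboratory toxicities will be tabulated (count and percentage) for each gradable parameter by the worst on-treatment NCI-CTC grade". The other is a shift table: "Shifts from baseline to worst NCI-CTC grade during the on-treatment period will also be tabulated". On the data that feed the worst grade, it says: "Measurements from both scheduled and unscheduled visits should be considered for the worst on-treatment grade derivation".

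For white-cell differentials, SAP 15.4 converts percentages to absolute counts "because the NCI-CTC grading is based on the absolute counts". It then covers one kind of missing range: "If the range for the differential absolute count is not available (only range for value in % is available"). In that case the percentage lower limit is used to assign Grade 1, on condition, among others, that the "derived absolute count does not meet Grade 2-4 criteria".

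**The concern.** A normal range matters to a toxicity grade only if the grading criterion uses it. SAP 15.4 treats Grade 2 to 4 for low neutrophil and lymphocyte counts as decidable from the count alone. SAP 7.1 nevertheless removes such a count from the shift tables whenever the external laboratory's range is missing.

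A worst grade is a maximum over the available values. Removing an on-treatment value from a maximum can leave it unchanged or lower it, but cannot raise it. Any error therefore runs towards understating toxicity. If the participant has other results, a lower worst grade may be shown. If there are none, the participant goes into the missing category that SAP 15.4 provides and stays in the denominator. Changes in laboratory parameters belong to a secondary safety endpoint of the study (Protocol 3; SAP 5), so the tables concerned are planned outputs.

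**Working it through.** The plan gives no figure on this point, so the check is a comparison of text with a short illustration.

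**1. Is the shift-to-worst-grade table covered by the exclusion?** SAP 7.1 admits external results to shift analyses only when ranges are present. The shift from baseline to worst grade in SAP 15.4 is a shift analysis. The exclusion is explicit.

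**2. Can a grade be given without the range?** For low neutrophil and lymphocyte counts, yes at Grade 2 to 4. SAP 15.4 tests those grades on the derived absolute count first and needs the percentage limit only to assign Grade 1. Its floors for Grade 1 are 1500/mm³ (neutrophils) and 800/mm³ (lymphocytes).

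Example with assumed values, using the formula in SAP 15.4:

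- Absolute count = white-cell count × percentage / 100.
- White-cell count 2000/mm³ with 20% neutrophils gives 2000 × 20 / 100 = 400/mm³.
- 400 is below 1500, so the value is too low for Grade 1 and must be Grade 2 or worse. No range was used. The exact grade depends on NCI-CTCAE cut-offs that the documents do not reproduce.
- If this result comes from an external laboratory without a range, SAP 7.1 still keeps it out of the shift table.

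**3. Is the frequency table covered as well?** The documents point both ways.

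| Points to exclusion | Points to inclusion |
|---|---|
| SAP 7.1 restricts these results to listings and summary statistics *only* | SAP 15.4 feeds scheduled and unscheduled measurements into the worst grade, with no exception for external laboratories |
| The opening of SAP 11 separates summary statistics (continuous) from frequency statistics (categorical) | SAP 11.6 uses the term summary statistics for a list that includes ECOG status, a categorical variable |
| | SAP 7.1 opens by saying that the pandemic leads to no change in the planned safety analysis |

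This cannot be settled from the text.

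**4. What would one omitted participant do?** The denominators are the planned cohort sizes in Protocol 9.2: 22 (Cohort A) and 20 (Cohort B). Assume that one participant's only Grade 3 or 4 value for a parameter is such a result, and that nobody else in the cohort has that grade. Intervals are exact Clopper-Pearson 95% limits, shown for scale only, since the SAP does not plan them for laboratory tables.

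| Cohort | Shown | With the value graded | Difference |
|---|---|---|---|
| A | 0/22 = 0% (0 to 15.4) | 1/22 = 4.5% (0.1 to 22.8) | 4.5 points |
| B | 0/20 = 0% (0 to 16.8) | 1/20 = 5.0% (0.1 to 24.9) | 5.0 points |

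**The case against.** The strongest reply is that little is lost. The result is still listed, and SAP 15.4 provides for CTCAE grades in the laboratory listings. If it comes from a scheduled visit, it also enters descriptive statistics that show the minimum and maximum. Protocol 8.2.4 has the investigator record clinically relevant laboratory changes as adverse events, and SAP 15.2.2 tabulates treatment-emergent events by worst grade. Protocol 8.2.4 also requires local laboratories to supply their normal ranges, which should keep the problem rare. All of this stands. It reduces the consequence but does not put the value into the shift table. An unscheduled result has less protection, because by-visit statistics use scheduled visits only (SAP 9).

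A reader might also infer more than the documents support:

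- *That SAP 7.1 and 15.4 contradict each other outright.* SAP 15.4 addresses the case where the absolute-count range is absent but a percentage range exists. SAP 7.1 addresses missing ranges from external laboratories in general. SAP 15.4 shows what can be graded without the absolute range; it does not give an opposite rule for the same situation.
- *That the exclusion is wrong for every parameter.* The documents show the point only for neutrophils and lymphocytes. SAP 15.4 names ALP, ALT, AST, bilirubin and creatinine as graded by their ratio to the upper limit of normal, and there the exclusion is reasonable.
- *That the SAP expects 10 or more participants to use external laboratories.* The figure of 10 in SAP 7.1 is a threshold for displaying a row, not a forecast, and it counts all external testing, not results without ranges.
- *That sicker participants use external laboratories more.* The documents do not say so. The one-way direction of the error does not depend on it.

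**Conclusion.** The point holds in a limited form. SAP 7.1 explicitly removes external results without ranges from the shift-to-worst-grade table for all parameters. For low neutrophil and lymphocyte counts at Grade 2 to 4, SAP 15.4 shows that the missing range is no obstacle to grading. For on-treatment values, the worst grade in that table can then be understated but not overstated.

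It would be tempting to conclude that a known severe value disappears from all worst-grade tables. The text does not establish that. Exclusion from the frequency table is one reading of an ambiguous sentence, and the two sections need reconciling.

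The size is unknown and may be zero, because the documents do not say how many results will lack a range. The 4.5 and 5.0 points are the effect of one affected participant, on the assumption that this participant has no other result of the same grade for that parameter. The study is descriptive and no decision rule rests on these tables, so this is a low-severity improvement worth making because it is cheap.

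**What to change.** Reword SAP 7.1 so that the exclusion covers only classifications that need the missing range:

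- Grade 0 versus Grade 1;
- parameters graded in multiples of the upper limit of normal, such as ALP, ALT, AST, bilirubin and creatinine;
- low/normal/high categories.

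State in the same place that external results gradable on an absolute cut-off enter both the worst-grade frequency table and the shift table under SAP 15.4. This means neutrophils and lymphocytes at Grade 2 to 4, and any other parameter whose criterion needs no range. It also settles the ambiguity about the frequency table.

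The cost is a sentence or two in the SAP and a small programming change before database lock. No new data are needed.

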8.1 Definition of Analysis Populations

The analysis populations are specified below. The final decision to exclude participants from any analysis population will be made during a data review meeting prior to database lock.

Screening Analysis Set (SCR)

The Screening analysis set includes all participants, who provided informed consent, regardless of the participant's study intervention status in the study.

Full Analysis Set (FAS)/ Safety Analysis Set (SAF)

These analysis sets will include all participants, who were administered at least one dose of any study intervention.

Dose Limiting Toxicity Analysis Set (DLT)

The Dose Limiting Toxicity analysis set (DLT) will include all participants who received at least one dose of study treatment in the safety run-in period and meet at least one of the following criteria:

- Received at least 75% of the tepotinib and cetuximab planned dose and complete the DLT period (3 weeks after start of treatment with study intervention).
- Experienced a DLT during the DLT period, regardless of the received amount of each study intervention.

Pharmacokinetics Analysis Set (PKAS)

The pharmacokinetics analysis set will include all participants, who received at least one dose of study intervention, have no relevant protocol deviations or important events affecting PK, and provide at least one measurable post-dose concentration. Participants will be analyzed per the actual study intervention they received.

Immunogenicity Analysis Set (IMAS)

All participants who receive at least one dose of study intervention and have at least one valid ADA result. Participants will be analyzed per the actual study intervention they received.

Analyses per Analysis Set

The following table summarizes the use of the analysis sets in the different analyses.

	Analysis Set				
Analyses	DLT	FAS	SAF	PK	IMAS
DLT	✓				
Baseline Characteristics		✓			
Previous and Concomitant Therapies		✓			
Compliance and Exposure			✓		
Efficacy: Primary		✓			
Efficacy: Secondary		✓			
Safety and Tolerability			✓		
PK				✓	
Immunogenicity					✓

DLT = Dose Limiting Toxicity; FAS = Full Analysis Set; SAF = Safety Analysis Set; PK = Pharmacokinetics; IMAS = Immunogenicity Analysis Set.

All safety analyses will be presented by cohort and dose level, if applicable. Efficacy analyses will be done by cohort and assigned dose level of tepotinib.

For more details see Section 0 General Specifications for Data Analyses.

8.2

Subgroup Definition and Parameterization

Subgroup analyses will be performed on the primary efficacy endpoint OR and the secondary efficacy endpoints DoR/PFS/OS as defined in [Table 1](#). All subgroup analyses will be exploratory, no adjustment for multiplicity will be performed. Endpoints for which subgroup analyses will be performed can be found in [Section 14](#). In case of low number of participants within a subgroup level (< 5 participants), levels will be pooled when meaningful.

For the definition of subgroup levels, data as documented in the electronic case report form (eCRF) or provided in the SDTM datasets will be taken. The category “missing” will not be included in any subgroup analysis.

Table 1. Subgroups

Subgroup	Subgroup level	Definition/ Derivation
Treatment line	
• 2nd line (Cohort A)• 3rd line• 4th line• 5th + line	CRF: PRIOR ANTI-CANCER DRUG THERAPIES DETAILS: Regimen number
Site location (Cohort B)	
• ACCRU sites• Other US sites	
Mutations in the extracellular domain of EGFR	
• Yes• No	The following mutations are of relevance and should be taken into account: F404, T414, V441, S442, I462, S464, G465, K467, K489, I491, S492
MET amplification (if available)	
• Focal• Non-focal	
MET amplification	
• Liquid• Tissue	CRF: TISSUE BIOPSY FOR MET

		AMPLIFICATION: MET amplification result
Prior EGFR therapy	
 • Panitumumab • Cetuximab 	
Time since last EGFR therapy in months	
 • 1 • 2 • > 2 	
HGF protein expression level (if available)	
 • < median • \geq median 	
Age group	
 • < 65 years • \geq 65 years 	
Race	
 • White • Black or African American • Asian • Not collected at this site • Other 	
 • White • Black or African American • Asian • Other (including American Indian or Alaska Native and Native Hawaiian or Other Pacific Islander) 
“Not collected at this site” will be handled as missing

Sex	
 • Male • Female 	
Brain metastases at baseline	
 • Present • Absent 	
ECOG at baseline	
 • 0 • 1 	

9 General Specifications for Data Analyses

This section describes any general specifications not included in subsequent sections.

Study treatment and study treatment component:

Participants will receive tepotinib (RP2D mg daily) in combination with cetuximab (loading dose (where required) 400 mg/m², followed by or starting with weekly infusions at a dose of 250 mg/m²).

In this IAP, “study treatment” will be used to indicate the combination of tepotinib and cetuximab; “study treatment component” will be used to refer to tepotinib or cetuximab.

Study treatment start date:

For each participant, the “start date” of this study is the date of first administration of the study treatment. If, for any reason, the first administration of tepotinib and cetuximab does not happen on the same day, the date of administration of the first study treatment component taken should be considered as the “start date”.

Study treatment end date:

The last tepotinib and cetuximab administration dates are collected on the “Tepotinib Termination” and “Cetuximab Termination” eCRF pages. These should be considered the dates of permanent discontinuation of tepotinib and cetuximab respectively.

The end of study treatment will be the last study tepotinib administration date or the last study cetuximab administration date, whichever comes later.

Dose Level:

As stated in Section 6.1, the SMC will decide whether the tepotinib 500 mg dose level is considered safe or if the 250 mg dose level should be used instead. Cetuximab will be administered as intravenous infusion as detailed in protocol Section 6.1.

Cohort:

Cohort A – includes participants outside of US for 2L treatment.

Cohort B – includes US participants for 3L+ treatment.

Presentation of analysis results:

Unless stated otherwise, for disposition, baseline characteristics (e.g. demographics, medical history, disease history, etc.), previous and concomitant medications and procedures, results will be presented by cohort, by assigned dose level of tepotinib and overall.

For efficacy analyses, results will be presented by cohort and assigned dose level of tepotinib.

Exposure and safety will be presented by cohort and dose level, if applicable, and overall.

Presentation of continuous and qualitative variables:

Continuous variables other than PK will be summarized using descriptive statistics, i.e.

- number of participants with non-missing values (n)
- mean, standard deviation (StDev)
- median, 25th percentile - 75th percentile (Q1-Q3)
- minimum, maximum

Mean, median, Q1, Q3, Min, and Max will have the same precision as collected in SDTM datasets for non-derived data. Standard deviation will be presented with one digit more than the mean. Percentage and percent change from baseline will be reported using one decimal digit, if not specified otherwise. Derived data such as duration and “time since” variables (see Section 9.4) will be displayed with one decimal digit, unless stated otherwise.

If there are no missing values, the number of participants with missing values should be indicated by a 0.

Qualitative variables will be summarized by frequency counts and percentages. Unless otherwise stated the calculation of proportions will be based on the number of participants in the analysis set of interest. Therefore, counts of missing observations will be included in the denominator and presented as a separate category.

For variables where a participant may have more than one category due to multiple responses per participant, the number of participants included in each category will be summarized as a percentage from all participants. Therefore, the total frequency across categories may not equal the total number of all participants in that analysis group.

Scheduled and unscheduled visits

Data collected at both scheduled and unscheduled visits will be included in the derivation of safety and efficacy endpoints.

Unscheduled visits will be included in the derivation of baseline or worst on-treatment values. Descriptive statistics by nominal visit or time point, e.g. for laboratory measurements, will include only data from scheduled visits

Significance level:

There is no formal significance level for this study, and all analyses are considered descriptive.

There will be no statistical tests performed. If confidence or credibility intervals are mentioned, the level will be 95% unless otherwise specified.

Statistical software:

All analyses will be performed using SAS® Software version 9.4 or higher.

